No major adverse effects have been associated with mild to moderate intermittent calorie restriction.^{39,40,94} Two of our previous CR studies did not have a reported serious AE incident.^{39,40} More severe caloric restriction in humans relative to our studies also produced no serious AEs⁹⁴. We classify the 5-2 CR and control diet as minimal risk.

8. Subject safety monitoring

8.a. Monitoring of Subjects

The investigator or clinical staff performing a study procedure will monitor subject safety. This includes physicians, licensed practitioners (NPs) and RNs during LPs, blood draws, mixed meal testing, and History and Physical sessions; investigators administering questionnaires and cognitive testing, MRI techs and investigators during MRIs.

The PI will make determinations regarding the presence and grading of on adverse events (AEs) and unanticipated problems (UPs). Whenever study investigators contact subjects throughout the study, they will seek information on AEs and UPs. AE's and UPs will also be elicited during study visits, by subjects filling in the symptoms review questionnaire or during history and physical examination. Participants will be asked to use electronic mail (Secure Email & File Transfer Service: <https://secureemail.nih.gov/bds/Login.do>) or telephone to inform the investigators about any AE's or UPs experienced. AEs and UPs may be observed by the Investigator and/or study staff, elicited from the subject and/or family member, or volunteered by the study subject. AEs and UP's that had previously been reported by study subject will also be reassessed for duration, intensity and

possible reoccurrence. Assessment of safety will include vital signs, history and physical sessions, questionnaires on physical and psychological symptoms and clinical labs as indicated. Any AE or UP that occurs between the times a study participant signs the informed consent form and the end of participation will be assessed and recorded under NIH HRPP SOP # 16 and 16 A.

In particular, we will monitor the weight loss of the participant. If a participant on 5-2 CR loses 4-5% of their body weight within a 2-week period between visits, additional safety visits will be scheduled every week to monitor body weight more closely. If weight loss in that range or greater continues to occur, participants will be removed from the study.

A study participant will also be discontinued from the study if:

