ATTACHMENT E. Symptoms Review Questionnaire for 5-2 CR participants

Symptoms Review Questionnaire

Intermittent Calorie Restriction

Since **last week**, on a 1-10 scale, please rate how you felt on **NON-CR DAYS** for:

	Less	→	More								
Amount of Energy	0	1	2	3	4	5	6	7	8	9	10
Ability to Concentrate	0	1	2	3	4	5	6	7	8	9	10
Constipation	0	1	2	3	4	5	6	7	8	9	10
Headache Severity (if any)	0	1	2	3	4	5	6	7	8	9	10
Feeling Cold	0	1	2	3	4	5	6	7	8	9	10
Feeling Sad/Depressed	0	1	2	3	4	5	6	7	8	9	10
Feeling Irritable	0	1	2	3	4	5	6	7	8	9	10
Feeling Anxious	0	1	2	3	4	5	6	7	8	9	10
Feeling Hungry	0	1	2	3	4	5	6	7	8	9	10
Preoccupation with Food	0	1	2	3	4	5	6	7	8	9	10

Since **last week**, on a scale from 1-10, please rate how you felt on **CR DAYS** for:

	Less	→	More								
Amount of Energy	0	1	2	3	4	5	6	7	8	9	10
Ability to Concentrate	0	1	2	3	4	5	6	7	8	9	10
Constipation	0	1	2	3	4	5	6	7	8	9	10
Headache Severity (if any)	0	1	2	3	4	5	6	7	8	9	10
Feeling Cold	0	1	2	3	4	5	6	7	8	9	10
Feeling Sad/Depressed	0	1	2	3	4	5	6	7	8	9	10
Feeling Irritable	0	1	2	3	4	5	6	7	8	9	10
Feeling Anxious	0	1	2	3	4	5	6	7	8	9	10
Feeling Hungry	0	1	2	3	4	5	6	7	8	9	10
Preoccupation with Food	0	1	2	3	4	5	6	7	8	9	10

Have you experienced any other symptoms that you did not have before going on the diet? If so, please write down those symptoms here:

Participant ID: _____

Investigator/Staff Name: _____

Date: _____

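### The only free-text question on both Symptoms Review Questionnaires is narrower than the protocol's own adverse-event window and does not fit Screening or Baseline

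*Combined protocol and SAP*

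**What the plan says.** Section 8.a (Monitoring of Subjects) gives the questionnaire a safety role: adverse events and unanticipated problems "will also be elicited during study visits, by subjects filling in the symptoms review questionnaire", or at history and physical examination. It sets the recording window just as plainly: any such event that "occurs between the times a study participant signs the informed consent form and the end of participation will be assessed and recorded".

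Attachment E holds two versions of the form, one for 5-2 CR participants and one for the healthy living arm. Each has ten symptoms scored 0 to 10 (the 5-2 CR version takes them twice, for restricted and unrestricted days) and then one open question, worded identically in both: "Have you experienced any other symptoms that you did not have before going on the diet".

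The form is scheduled at Screening (section 4.c, Table 1), Baseline (section 4.d.2, Table 1) and Outcome (section 4.d.5, Table 1). Section 4.d.4 also has it completed at the Compliance Visits of weeks 2, 4 and 6, but Table 1 does not mark it there.

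**The concern.** The open question takes the start of the diet as its reference point, whereas the recording window opens at consent. A participant who answers literally leaves out two kinds of event when the symptom is not one of the ten rated items: one that began after consent but before the diet, and an existing complaint that has become worse or come back.

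The discontinuation criterion in section 8.a (Grade 2 or greater and possibly related) and the enrolment-suspension criterion in section 15.c (related, grade 3 or higher) can act only on events that reach the investigator. A form named as an elicitation tool should not steer participants away from reporting events that the protocol wants recorded. The same mismatch makes the answers given at the two pre-diet visits uninterpretable.

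**Working it through.** No formula applies, and the plan states no figure on this point. The check sets the forms beside the safety section and the visit schedule.

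1. **Reference point against window.** Attachment E: symptoms absent before the diet. Section 8.a: consent to end of participation. Section 4.d.3 assigns the diet at the end of the Baseline Visit, so everything from consent to that moment is inside the window but outside the question. Section 4.d.2 and Table 2 allow up to four weeks between Screening and Baseline (section 4.d.1 says three), and Baseline procedures may be split over two days up to a week apart.

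2. **What happens in that interval.** The mixed meal test, intravenous line, MRI and lumbar puncture of the Baseline Visit come before diet assignment. Sections 7.i and 7.j list gastrointestinal upset, bruising, infection, haematoma and CSF leak among their risks. None of these is a rated item. Headache, the one lumbar puncture effect given a rate (about 5% at least), is rated.

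3. **Which tools are in use at Baseline.** Section 8.a names two tools for eliciting events at visits: "by subjects filling in the symptoms review questionnaire or during history and physical examination". Table 1 marks history and physical only at Screening and Outcome. At Baseline the questionnaire is therefore the only one of the two in use, alongside general staff inquiry.

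4. **Fit to the schedule.** By Table 1 the form is used three times, two of them before the diet. Adding the Compliance Visits of section 4.d.4 gives 3 + 3 = 6 uses, again two before the diet. Both attached versions are specific to an arm, and no pre-diet version is attached.

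5. **Worsening.** The ten items are scored whether or not the symptom was there before, so a change in energy, concentration, constipation, headache, feeling cold, mood, irritability, anxiety, hunger or food preoccupation can be seen against the Baseline form. The gap concerns unlisted complaints only. Section 8.a does follow up events that had "previously been reported by study subject will also be reassessed for duration, intensity and" recurrence, but that covers only events already reported.

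6. **Dating.** Each form carries its own date but has no field for when a symptom began.

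**The case against.** The strongest reply is that the form is only one route among several. Section 8.a also says: "Whenever study investigators contact subjects throughout the study, they will seek information on AEs and UPs". Events may be observed by staff, "elicited from the subject and/or family member, or volunteered by the study subject". Participants are asked to report by email or telephone, and vital signs and laboratory results contribute. Section 4.a.2 adds contacts at weeks 1, 3, 5 and 7, and section 7.j keeps participants under observation for three hours after a lumbar puncture. If the Baseline Visit is not split, the time from lumbar puncture to diet start is probably short. All of this stands. A reader might infer from the form that these events go unelicited in the trial; the documents do not support that. They show only that this question does not ask.

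A second reply is that no passage defines an adverse event as including worsening of an existing condition. Recording is referred to NIH procedures that are not part of these documents. This also stands: the obligation to record is explicit for the interval from consent to diet, and only implied for worsening.

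A third tempting step is to put a number on the loss. Section 7.p expects minor events in 9–15% of participants, which is 0.09 × 20 = 1.8 to 0.15 × 20 = 3.0 people in an arm of 20, so one missed person would be 1/20 = 5 percentage points. That does not follow. The events behind the 9–15% (lethargy, feeling cold, poor concentration, irritability) correspond to rated items and do not depend on the open question. Section 10.a plans no comparison of adverse-event counts by arm.

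Finally, the attached versions may be meant for on-diet use only. If so, the mismatch at Screening and Baseline is a missing pre-diet form, which still needs to be supplied.

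**Conclusion.** The point holds in a limited form. The only free-text question on a named elicitation tool is narrower than the recording window in section 8.a, for symptoms outside the ten rated items, and it cannot be answered meaningfully at Screening or Baseline. The part concerning the interval from consent to diet is the firmer one, because the window is explicit. The part concerning worsening assumes that any adverse event includes worsening of an existing complaint.

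The documents give no rate of unlisted, pre-diet or worsening events and no capture rate for the other routes, so the size cannot be stated. Nothing shows that a Grade 2 or grade 3 event would surface only through this question. With staff inquiry at every contact behind it, this is a minor improvement. It is worth making because it costs almost nothing.

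**What to change.** At Baseline and every later visit at which the form is used, in both arms, replace the open question with: *Since your last visit or contact, have you had any new symptom, or has any symptom or condition you already had become worse or come back? When did it start?*

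At Screening, use a version that records existing symptoms as the pre-study reference. The since-last-visit wording does not suit that visit, because consent is first given there and the answers would be history from before consent.

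Reconcile section 4.d.4, which has the form completed at Compliance Visits, with Table 1, which does not mark it there.

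The cost is a short form revision and one extra version. The downside is a few more entries for the investigators to review.

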ATTACHMENT E. Symptoms Review Questionnaire for “Healthy Living Diet” participants

Symptoms Review Questionnaire

Healthy Living Diet

Since **last week**, on a scale from 1-10, please rate these items for how you felt

	Less	→	More
Amount of Energy	0	1	2 3 4 5 6 7 8 9 10
Ability to Concentrate	0	1	2 3 4 5 6 7 8 9 10
Constipation	0	1	2 3 4 5 6 7 8 9 10
Headache Severity (if any)	0	1	2 3 4 5 6 7 8 9 10
Feeling Cold	0	1	2 3 4 5 6 7 8 9 10
Feeling Sad/Depressed	0	1	2 3 4 5 6 7 8 9 10
Feeling Irritable	0	1	2 3 4 5 6 7 8 9 10
Feeling Anxious	0	1	2 3 4 5 6 7 8 9 10
Feeling Hungry	0	1	2 3 4 5 6 7 8 9 10
Preoccupation with Food	0	1	2 3 4 5 6 7 8 9 10

Have you experienced any other symptoms that you did not have before going on the diet? If so, please write down those symptoms here:

Participant ID: _____

Investigator/Staff Name: _____

Date: _____

26. Consent forms

Please see attached consent forms for healthy adult volunteers.
